#### *Effects of Cannabidiol on the inflammasome:*

While the exact molecular mechanisms by which cannabidiol modulates inflammasome signaling has not been investigated completely, the current evidence supports their importance as promising therapy to regulate inflammasome signaling.(Suryavanshi, Kovalchuk, and Kovalchuk 2020)

The first report on the direct effect of CBD on the inflammasome came in 2016 from a group of Italian researchers.(Libro et al. 2016) They treated human gingival mesenchymal stem cells (hGMSCs) for 24 h with CBD (5 mM) and performed gene expression analysis and immunocytochemistry. They discovered that CBD-treated hGMSCs suppressed NLRP3, caspase-1, and IL-18 at the gene and protein levels and inhibited NF-κB. As NF-κB is involved in the priming of the NLRP3 inflammasome, the

CBD treatment– induced inactive state of the NLRP3 inflammasome in hGMSCs suggested that CBD-treated gingival stem cells were more immunocompetent, avoiding the risk of inflammatory reactions and promoting survival. Mice fed with a high-fat, high cholesterol (HFC) diet for 8 weeks showed significantly higher expressions of NLRP3 inflammasome pathway proteins (NLRP3, ASC, IL-1 $\beta$ , and caspase-1) in the liver; these proteins were significantly attenuated by simultaneous treatment with CBD (5 mg/kg/day for 8 weeks). Similarly, the phosphorylation of NF- $\kappa$ B was significantly reduced in the liver of CBD-treated HFC mice compared to the non-treated group, corroborating the role of NF- $\kappa$ B in priming the NLRP3 inflammasome. To further confirm the role of the inflammasome in liver inflammation, the authors studied the effect of CBD on an LPS + ATP treated mouse macrophage cell line, confirming with *in vivo* data that the expressions of NLRP3, ASC, IL-1 $\beta$ , NF- $\kappa$ B, and caspase-1 were lower in CBD-treated cells. (Huang et al. 2019) Mouse microglial cells treated with LPS to simulate neuroinflammatory conditions exhibited a robust activation of pro-inflammatory cytokine repertoire, and CBD (1–10 mM) was able to suppress the secretion of IL-1 $\beta$  and inhibit the NF- $\kappa$ B signaling pathway.(Dos-Santos-Pereira et al. 2019).

In an *in vitro* skin inflammation model, human keratinocytes were treated with ultraviolet rays A and B (UVA and UVB) and treated with CBD (1 mM) for 24 h. CBD inhibited protein-protein interaction between nuclear factor erythroid 2-related factor 2 (Nrf2) and NF- $\kappa$ B in UVA- and UVB-treated skin cells. CBD increased NRF2 expression, leading to decreased reactive oxygen species (ROS), which in turn may have partially suppressed NLRP3 inflammasome activation by reducing NF- $\kappa$ B levels.(Jastrząb, Gęgotek, and Skrzypieńska 2019). Beta Amyloid induced neurotoxicity (G Esposito et al. 2007) and the severity of inflammatory colitis (Borrelli et al. 2009) were significantly suppressed by CBD treatment in mice partly due to inhibiting the expression and release of IL-1 $\beta$ .

A significant reduction of IL-1 $\beta$  by CBD treatment in a murine viral model of multiple sclerosis was also shown, suggesting its role in combating inflammation in multiple sclerosis. (Mecha et al. 2013) Recently, CBD was shown to inhibit NLRP3 inflammasome by reducing K+ efflux by binding to the P2X7 receptor in human monocytes.(Liu et al. 2020) Remarkably, the fact that only CBD (non-psychoactive), not tetrahydrocannabinol (THC) (psychoactive), was found to inhibit NF $\kappa$ B signaling (Rimmerman et al. 2011), coupled with the direct proven inhibitory action of CBD on inflammasomes (Huang et al. 2019) and downstream proteins, indicates the incomparable potential of CBD as an inflammasome-inhibitory drug target.

Evidence of an effect of CBD on inflammatory markers in humans is limited. A recent randomized controlled trial studied the effects of 12 weeks of 800 mg/day of pure CBD on inflammatory markers in 48 individuals with cocaine use disorder. It was seen that, compared to participants receiving placebo (n = 24), those participants treated with CBD (n = 24) had significantly lower levels of IL-6 (p = 0.017), vascular endothelial growth factor (VEGF; p = 0.032), intermediate monocytes CD14+CD16+ (p = 0.024), and natural killer CD56negCD16hi (p = 0.000).(Morissette et al. 2021) An earlier clinical study in patients with type 2 diabetes assessed CBD effects on three inflammatory

markers: IL-6, CRP, and tumor necrosis factor- $\alpha$  (TNF- $\alpha$ ). The authors found no significant difference between the CBD (n = 13) and placebo (n = 14) groups on these markers with 100 mg CBD twice daily for 13 weeks; however, this dose is low compared to other human studies (Bergamaschi et al. 2011; Leweke et al. 2012; Morissette et al. 2021) that use higher doses of CBD (600 – 800 mg/day), which may explain lack of therapeutic effects seen with CBD in this study.(Jadoon, Tan, and O'Sullivan 2017)

*Effects of CBD on models of CV inflammation including pericarditis:*

CBD improves endothelial function, and endothelial dysfunction is an important therapeutic target in a number of CV diseases including heart failure. CBD reduces inflammatory activation of the endothelial lining of blood vessels (Rajesh et al. 2007) thus improving endothelial vaso-relaxation (Stanley et al. 2015; Saoirse E. O'Sullivan et al. 2009) and blood flow. CBD has also been shown to attenuate a number of measures of potential importance in the treatment of heart failure, including cardiac dysfunction, oxidative stress, fibrosis, and inflammatory and cell death signaling pathways in models of diabetes (Rajesh et al. 2010), a common co-morbidity in CV disease patients. CBD has also been shown to be protective against doxorubicin (DOX)-induced cardiotoxicity, including reducing pro-inflammatory responses in the heart.(Fouad et al. 2013; Hao et al. 2015)

A murine model of experimental autoimmune myocarditis (EAM) induced by immunization with the myocarditogenic cardiac myosin peptide ( $\alpha$ MHC334–352) resulted in T cell infiltration into the myocardium, T cell-mediated inflammation, cardiomyocyte cell death, fibrosis and myocardial dysfunction. In this model, chronic treatment with CBD (10 mg/kg, ip for 46 days) reduced the infiltration of the myocardium by inflammatory cells, decreased myocardial inflammation as reflected by lowered levels of inflammatory cytokines and chemokines (IL-6, IL-1 $\beta$ , IFN-gamma, MCP1), reduced markers of oxidative stress and reduced myocardial fibrosis.(Lee et al. 2016)

The effect of CBD was also investigated on the cardiomyocyte cell line H9c2. H9c2 cells respond to angiotensin II by increasing in size, reflecting the myocardial hypertrophy seen in heart failure. The surface area of cultured cardiomyocytes is significantly increased by angiotensin II, and this increase is significantly decreased by CBD. Similarly, the expression of both BNP and collagen by H9c2 cells is significantly increased by angiotensin II and, again, this increase is prevented by CBD (Cardiol Therapeutics, unpublished data). In conclusion, CBD reduces the deleterious effect of angiotensin II on cardiomyocytes, including abrogating increases in cardiomyocyte size and the expression of remodeling markers.

In addition, the animal model of heart failure in male C57BL/6 mice, based on the published method of Cordero-Reyes has been used to assess CBD effectiveness.(Cordero-Reyes et al. 2016) This is a model of cardiac inflammation with associated depression of myocardial function. The results show that CBD reduced

inflammation and fibrosis induced by angiotensin-II in this model of heart failure. Measurements of myocyte area showed that CBD administered by sub-cutaneous injection resulted in a significant reduction at doses of both 1 and 10 mg/kg. Measurements of BNP, which is released from cardiomyocytes in response to excessive stretching and is elevated in heart failure, showed that CBD reduced expression of BNP in heart failure hearts.(Lozano et al. 2020) In conclusion, CBD administered by subcutaneous injection reduced a number of markers reflecting heart failure in this model system.

Cardiol Therapeutics is currently conducting a trial in patients with acute myocarditis (IND 145215). A trial in patients with COVID-19 at high CV risk (IND 152096) has been discontinued due to a lack of eligible hospitalized COVID-19 patients.

The efficacy of cannabidiol has been tested in a mouse model of acute pericarditis that was developed to investigate whether the pathophysiology of acute pericarditis is linked to a virus or another irritant activating the NLRP3 inflammasome, leading to IL-1 $\beta$  release, COX-2 activation, and prostaglandins production. (Mauro et al. 2021) The model uses zymosan A, a product of the yeast wall that activates NLRP3, injected directly into the pericardial space. Pericardial inflammation is measured by echocardiography (pericardial effusion) and at pathology (pericardial thickening, expression of the NLRP3 inflammasome component ASC). Results have demonstrated that cannabidiol treatment significantly reduces the pericardial effusion and pericardial thickening induced by zymosan A in this model.

Additional *in vitro* models using activated murine macrophages have demonstrated cannabidiol's ability to significantly inhibit release of the inflammatory cytokines IL-1 $\beta$  and IL-6, and significantly inhibit transcription of NLRP3 and pro-IL-1 $\beta$ . Together, these results suggest cannabidiol plays a role in attenuating multiple inflammatory pathways, including inhibiting activation of the NLRP3 inflammasome. These results have been presented at and the American Heart Association Scientific Sessions 2022. (Martinez-Naya 2022). This model has been used previously to demonstrate the efficacy of colchicine, IL-1 blockers anakinra and rilonacept, and NLRP3 inhibitors in reducing pericardial effusion and thickening. Cannabidiol has now also been shown to significantly reduce pericardial effusion and thickening in this mouse model of acute pericarditis, suggesting cannabidiol may represent a novel strategy for treating pericarditis, its complications, and preventing its recurrence.

*Unmet need:*

The recent US Database Study (A. Klein et al. 2021) found the most-commonly prescribed treatments for a first episode were colchicine alone (12%), or with NSAIDs (14%). Second, third, fourth, and fifth episodes were most-commonly treated with colchicine alone, corticosteroids alone, or another drug (not colchicine, corticosteroid, or NSAID; included intravenous immunoglobulin, azathioprine, methotrexate, and cyclosporine). The percentage of patients receiving something other than

corticosteroids, NSAIDs, or colchicine, alone or in combination, rose from 4% in the first episode up to 17% in the fourth episode and 15% in the fifth episode. This data was collected prior to the publication of the RHAPSODY trial and subsequent approval of rilonacept by the FDA for treatment of recurrent pericarditis and reduction in risk of recurrence.(A. L. Klein, Imazio, et al. 2021)

The low level of utilization of colchicine is likely due to a multitude of factors. Colchicine has a narrow therapeutic window with risk of fatal overdose, significant drug interactions, and neuromuscular toxicity. In addition, approximately 10% to 15% of patients experience significant gastrointestinal (GI) side effects with colchicine, including GI intolerance or severe diarrhea, requiring treatment discontinuation.(Cremer et al. 2016) Colchicine resistance likely leads to its use being abandoned in many patients.

The ESC guidelines stipulate that corticosteroids should be prescribed for the management of pericarditis episodes only in cases of incomplete response, intolerance, or contraindications to NSAIDs and colchicine because of their unfavorable long-term benefit-risk profile. Corticosteroid use is associated with side effects, including weight gain, diabetes, osteoporosis, avascular bone necrosis, and increased risk for infections.(Massimo Imazio et al. 2008) For the management of pericarditis, corticosteroids are usually administered at low to moderate doses and can provide rapid control of symptoms. However, they often require many months of tapering after the normalization of CRP levels. In addition, there is a high rate of pericarditis relapse when corticosteroid use is tapered or stopped (Maisch et al. 2004; Lotrionte et al. 2010), particularly in the absence of concurrent colchicine treatment.

Patients with recurrent pericarditis who are refractory or intolerant to current therapeutic management options or who require long-term administration of corticosteroids to control their disease can be particularly challenging to manage. While rilonacept is now available to some of these patients, its uptake has been low and there is the need for a safe, well tolerated, oral, accessible medication to add to the therapeutic options for these patients.

*Rationale for pilot study:*

This pilot study is to assess the tolerance and safety of CardiolRx™ during the resolution of pericarditis symptoms, evaluate improvement in objective measures of disease, and during the extension period assess the feasibility of weaning concomitant background therapy including corticosteroids while taking CardiolRx™. The results of this trial will inform the feasibility of designing a randomized double blind withdrawal trial to assess the effects of CardiolRx™ vs placebo in the treatment and prevention of recurrent pericarditis.

## 4 STUDY OBJECTIVES

### 4.1 *Efficacy*

#### 4.1.1 Primary Objective

The primary objective is to evaluate the effect of treatment with CardiolRx™ on recurrent pericarditis.

#### 4.1.2 Primary Efficacy Endpoint

The primary efficacy endpoint is patient-reported pericarditis pain using an 11-point NRS pain score, validated across multiple conditions with acute and chronic pain (Dworkin et al. 2005; Mannion et al. 2007; Hawker et al. 2011) from baseline (highest pain score within the past 7 days of Day 1) to Week 8 (highest pain score during the past 7 days of Week 8).

#### 4.1.3 Additional Efficacy Parameters of Interest

- Pain score using 11-point NRS from baseline (highest pain score within the past 7 days of Day 1) to Week 26 (highest pain score during the past 7 days of Week 26)
- Percentage of patients with normalized CRP levels at 8 weeks (for patients with CRP  $\geq 1.0$  mg/dL at baseline)
- Percentage of patients with pericarditis recurrence during the EP
- Percentage of patients with normalized CRP levels at 26 weeks (for patients with CRP  $\geq 1.0$  mg/dL at baseline)
- Time to CRP normalization for patients with CRP  $\geq 1.0$  mg/dL at baseline
- CRP change from baseline at 26 weeks (%)

### 4.2 *Safety*

#### 4.2.1 Safety Objective

The primary safety objective is to demonstrate that administration of CardiolRx™ in the proposed doses in this patient population is safe.

#### 4.2.2 Safety Parameters

Safety parameters include the number of AEs and SAEs, changes in C-SSRS as well as changes in laboratory parameters, including liver function parameters and INR as well as ECG intervals and rhythm during the 26-week study period.

## 5 STUDY POPULATION

### 5.1 *Enrolment and Study Centers*

Approximately 25 patients will be enrolled in multiple centers.

### 5.2 *Inclusion Criteria*

The following inclusion criteria must be met to enroll a patient into this study:

1. Male or female 18 years of age or older
2. Diagnosis of at least two episodes of recurrent pericarditis\*,  
3. At least 1 day with pericarditis pain  $\geq 4$  on the 11-point NRS within prior 7 days
4. One of:
  - a. CRP\*\* level  $\geq 1.0$  mg/dL within prior 7 days **OR**
  - b. Evidence of pericardial inflammation assessed by delayed pericardial hyperenhancement on CMR
5. Currently receiving NSAIDs and/or colchicine and/or corticosteroids for treatment of pericarditis (in any combination) in stable doses
6. Male patients with partners of childbearing potential who have had a vasectomy or are willing to use double barrier contraception methods during the conduct of the study and for 2 months after the last dose of study drug.
7. Women of childbearing potential willing to use an acceptable method of contraception starting with study drug administration and for a minimum of 2 months after study completion. Otherwise, women must be postmenopausal (at least 1 year absence of vaginal bleeding or spotting and confirmed by follicle stimulating hormone [FSH]  $\geq 40$  mIU/mL [or  $\geq 40$  IU/L] if less than 2 years postmenopausal) or be surgically sterile.

\* Diagnosis of pericarditis according to the 2015 ESC Guidelines for the Diagnosis and Management of Pericardial Diseases (Adler et al. 2015):

At least two of:

- a. Pericarditic chest pain
- b. Pericardial rub
- c. New widespread ST-segment elevation or PR-segment depression according to ECG findings
- d. Pericardial effusion (new or worsening)

\*\* Conversion: 1 mg/dL CRP = 10 mg/L hs-CRP

### **5.3 Exclusion Criteria**

Patients meeting any of the following criteria will be excluded from the study:

1. Diagnosis of pericarditis that is secondary to specific prohibited etiologies, including tuberculosis (TB); neoplastic, purulent, or radiation etiologies; post-thoracic blunt trauma (e.g., motor vehicle accident); myocarditis
2. Estimated glomerular filtration rate (eGFR) <30 mL/min
3. Elevated alanine aminotransferase (ALT) or aspartate aminotransferase (AST) > 5 times the upper limit of normal (ULN) or ALT or AST >3x ULN plus bilirubin >2x ULN
4. Sepsis, defined as documented bacteremia at the time of screening or other documented active infection
5. Prior history of sustained ventricular arrhythmias
6. History of QT interval prolongation
7. QTc interval > 500 msec (please refer to Section 9.2.3 for bundle branch block, bifascicular block and paced rhythm correction)
8. Current participation in any research study involving investigational drugs or device
9. Inability or unwillingness to give informed consent
10. Ongoing drug or alcohol abuse
11. On any cannabinoid during the past month
12. Women who are pregnant or breastfeeding
13. Current diagnosis of cancer, with the exception of non-melanoma skin cancer
14. Any factor, which would make it unlikely that the patient can comply with the study procedures
15. Showing suicidal tendency as per the C-SSRS, administered at screening
16. On digoxin and/or type 1 or 3 antiarrhythmics
17. On immunosuppressive therapy with any of the following:
  - a. Rilonacept
  - b. Anakinra
  - c. Canakinumab
  - d. Methotrexate
  - e. Azathioprine
  - f. Cyclosporine
  - g. IVIG

## 6 STUDY DESIGN

### 6.1 *Summary of Study Design*

Multi-center, open label Pilot Study.

Patients who present with recurrent pericarditis will be screened and informed consent obtained.

Baseline assessments include the following: Clinical assessment, including vital signs, pain score NRS, 12-lead ECG; C-SSRS as well as hematology and blood chemistry and a pregnancy test for women with child-bearing potential. If CRP was measured within 7 days of Day 1, this value will be used as the baseline value. If there is no CRP measurement available within 7 days of Day 1, CRP needs to be measured at baseline.

Concomitant medications are recorded and any (S)AEs after informed consent has been obtained.

Study treatment will be initiated in the evening of Day 1, after all baseline assessments are completed.

Oral administration (accompanied by food) is as follows:

- Initial starting dose (Day 1 p.m. dose to Day 3 a.m. dose):  
5 mg/kg of body weight CardiolRx™ b.i.d.
- Day 3 p.m. dose to Day 10 a.m. dose:  
7.5 mg/kg of body weight CardiolRx™ b.i.d.
- Day 10 p.m. dose to end of treatment period (a.m. dose at week 26):  
10.0 mg/kg of body weight CardiolRx™ b.i.d.
- The morning and evening doses should be taken minimally 6 hours and maximally 18 hours between each intake.

If the next higher dose after each study drug increase is not tolerated, the dose will be reduced to the previous tolerated dose.

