## **6.6 Concomitant Treatments**

Patients must be on SOC treatments for pericarditis with either NSAIDs, colchicine, or corticosteroids (in any combination) for at least 72 hours prior to Day 1. Unless contraindicated, these SOC treatments will be weaned during the 18 weeks EP as follows:

NSAIDs will be weaned within 2 weeks after the EP entry and corticosteroids within 6 weeks of EP entry (by 5 mg prednisone or equivalent every week).

For patients not taking corticosteroids, colchicine will be weaned between 2 and 4 weeks of EP entry, and for those on corticosteroids, colchicine weaning will be between 6 and 8 weeks of EP entry. Should it become evident that weaning of colchicine leads to high levels of pericarditis recurrence, the study leadership and the sponsor may decide colchicine weaning will no longer be performed during the EP.

Patients will not be allowed to be on immunosuppressive therapy with rilonacept, anakinra, canakinumab, methotrexate, azathioprine, cyclosporine, mycophenolate and/or IVIG and cannot take any cannabinoids during the study period nor strong inducers of CYP3A4 and CYP2C19 (see Section 17.7).

Use of digoxin and/or type 1 or 3 antiarrhythmics is an exclusion criterion for the trial. No drugs that are known to prolong QTc intervals should be started during the study (Appendix 17.6).

Also, because CardiolRx™ is known to inhibit the metabolism of certain other drugs, new symptoms or findings may represent toxicity from a concomitant medication that

had previously been well tolerated. Please refer to Section 6.3 of the Investigator Brochure (IB) and to Appendix 17.8.

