#### Visit 1 (Screening and baseline assessments – within 72 hours of Day 1)

The following evaluations will be performed a baseline:

- Written informed consent
- Demographics
- Medical History/Current conditions, including prior CV events and interventions
- Clinical assessment
- Vital signs, including heart rate (HR), blood pressure, body height and weight
- Collect highest NRS pain score within the past 7 days of DAY 1
- 12-lead ECG
- C-SSRS
- Collection of concurrent medication and medication history for the previous 1 month
- Local laboratory assessments, including CRP\*, CBC, AST/ALT, alkaline phosphatase, bilirubin, creatinine/eGFR, INR, pregnancy test (in women with childbearing potential)
- AE and SAE recording after informed consent has been obtained
- Assign study treatment to the patient

\* only if no measurement within 7 days of Day 1 is available

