#### **9.2.7 Collection of NRS Scores**

Patients will be asked to enter their pain scores into a diary on a daily basis using the 11-point NRS. Patients will have the choice to complete the NRS scale either on paper or in an electronic patient reported outcomes platform – i.e., eSOC DAT Patient Portal. Access to the eSOC DAT Patient Portal is restricted to authorized users only. State-of-the-art procedures are in place to prevent unauthorized access and data corruption, namely, firewalls, up-to-date virus scanning in addition to the encryption of data stored in the database and transmitted via the Internet. Patients will be provided with a unique username and password to access the eSOC DAT Portal.

In addition, the highest NRS pain score within the past 7 days will be recorded at baseline (patient recall) and at each visit after randomization from the Patient Portal entries/diaries or, if not available, from patient recall.

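### Baseline pain and CRP can date from before background therapy (7-day window against a 72-hour requirement), so a response before the first dose can be counted as change on CardiolRx

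*Protocol*

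**What the plan says.** - **Baseline pain.** Protocol 4.1.2 measures the primary endpoint "from baseline (highest pain score within the past 7 days of Day 1) to Week 8". Protocol 9.2.7 takes the baseline score from patient recall; the SAP keeps the same definition (2.3.1, 8.3.8).
- **Baseline CRP.** Protocol 6.1: "If CRP was measured within 7 days of Day 1, this value will be used as the baseline value". The Visit 1 footnote has CRP drawn "only if no measurement within 7 days of Day 1 is available", and Appendix 17.2 footnote 10 agrees. After that, the next scheduled CRP is at Visit 4 (Week 3).
- **Background therapy.** Protocol 6.6 requires NSAIDs, colchicine or "corticosteroids (in any combination) for at least 72 hours prior to Day 1". Inclusion criterion 5 reads "Currently receiving NSAIDs and/or colchicine and/or corticosteroids for treatment of pericarditis (in any combination) in stable doses", with no duration. The synopsis entry on concomitant treatments says only that therapy precedes Day 1.
- **Choice between two values.** SAP 8.3 takes the pre-dose value closest to the first dose. SAP 7 summarizes a qualifying CRP as well as a baseline CRP.
- **Analysis.** Single arm, descriptive only (Protocol 11.2, SAP 8.5). No table separates patients by when background therapy began.

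**The concern.** With no comparator, change from baseline is the whole efficacy result, so baseline should describe the patient just before the first CardiolRx dose, on the background therapy then in use. The two windows do not secure this. A patient may have a pain peak and a raised CRP on Day −6, begin background therapy on Day −4, and take the first dose on Day 1. The peak is then the starting point for every NRS change, and the early CRP is the starting point for percent change, normalization and time to normalization. The protocol gives a reason to expect movement in between for at least one drug class: "corticosteroids are usually administered at low to moderate doses and can provide rapid control of symptoms" (3.5, on unmet need).

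For CRP the loss may be irrecoverable, because no required measurement lies between the early value and Week 3. A patient already at or below 0.5 mg/dL on Day 1 who stays there counts as normalized on drug. The results are meant to inform a randomized withdrawal trial (Protocol 3.5) and to be set beside rilonacept trial data (SAP 8.5.3), so an inflated change would carry forward.

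**Working it through.** The plan states no effect size and no calculated sample size, so there is no figure to reproduce. The check compares the windows and then illustrates what could follow.

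**1. Windows (from the documents).** Baseline window 7 × 24 = 168 h. Minimum background therapy 72 h. Gap 168 − 72 = 96 h, which is 4 of 7 days, or 57%. This is a share of days, not of effect.

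**2. CRP (assumed kinetics).** Suppose CRP falls toward 0.3 mg/dL with half-time h days after background therapy starts, 72 h before the first dose. CRP at first dose = 0.3 + (C₀ − 0.3) × 2^(−3/h).

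| Early CRP C₀ (mg/dL) | h = 1 day | h = 4 days |
|---|---|---|
| 1.0 | 0.39 (61% fall) | 0.72 (28% fall) |
| 2.0 | 0.51 (74% fall) | 1.31 (34% fall) |
| 5.0 | 0.89 (82% fall) | 3.09 (38% fall) |

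Under these assumptions 28–82% of the early value is gone before the first dose. A patient entering at 1.0 mg/dL could already meet the SAP's normalization cut-off of 0.5 mg/dL. For percent change, take an invented patient with an early CRP of 3.0, Day 1 value 1.5 and Week 8 value 0.5: (0.5 − 3.0)/3.0 = −83%, against (0.5 − 1.5)/1.5 = −67% from Day 1.

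**3. Mean pain (assumed).** Inflation of the mean = share affected × pre-dose fall. At the low end 0.10 × 2 = 0.2 points; at the high end 0.50 × 4 = 2.0 points. Neither the shares nor the falls come from the documents.

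**4. Simulation with no CardiolRx effect (assumed).** Mean pain 6.5, daily SD 1, background effect 1–4 points with half-time 1 or 3 days, and 7-day maxima at baseline and Week 8.

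- Background therapy started 72 h before Day 1: apparent Week 8 change per affected patient −0.8 to −0.9 (effect 1), −1.7 to −1.8 (effect 2), −2.7 to −2.8 (effect 3), −3.7 to −3.8 (effect 4).
- Started 14 days before: 0 to −0.4.
- Started 72 h before, baseline cut to the last 3 days: about 0 to −2.6. Shortening the window alone is therefore not a repair, and it would also compare a 3-day maximum with a 7-day maximum.

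The first set includes response that continues after the first dose, which no choice of window removes. By the first dose the background effect has reached 1 − 2^(−3/1) = 87.5% or 1 − 2^(−3/3) = 50% of its full size, so for a 2-point effect the pre-dose part is 1.75 or 1.0 points. At 25% affected and 1.8 points each, the mean apparent change is 0.25 × 1.8 = 0.45 points.

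**5. Existing safeguards.** The closest-value rule in SAP 8.3 needs a second CRP, which the protocol does not require. Where a site draws one anyway, Protocol 6.1 and SAP 8.3 can select different baselines. The medication–NRS correlation in SAP 8.5.3 does not refer to start dates.

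**The case against.** The strongest reply is that the affected group may be small. Criterion 5 asks for stable doses, entry needs at least two episodes, and the rationale describes patients who are refractory, intolerant or on long-term corticosteroids. Many may have been on unchanged therapy well before the window. This stands: the documents neither give the share nor bound it.

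The supporting text is also narrower than it looks. A reader might cite Protocol 3.1, on pericarditis lasting days to weeks, as evidence of rapid resolution here. That passage describes patients with a single episode, and the next paragraphs contrast them with the recurrent group that this trial enrols. The remark on rapid symptom control concerns corticosteroids, not NSAIDs or colchicine.

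A reader might also infer that no second pre-dose CRP can exist. The documents say only that none is required when a value within 7 days is available. SAP 8.3.2 counts the qualifying 7 days from screening, and Visit 1 may fall up to 72 hours before Day 1. On that reading a qualifying value from 8 to 10 days before Day 1 would trigger a new draw, and nothing forbids a repeat.

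Finally, continuing response to background therapy is inherent in an uncontrolled add-on pilot, and the plan claims no inference. The SAP also tabulates days from diagnosis to first dose and baseline pericarditis medication, and it reviews the Amendment 1 patients (whose criterion specified 3 days) against the current criterion. These give context, but none separates patients whose baseline predates their background therapy.

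**Conclusion.** The mismatch is real: up to 96 of the 168 baseline hours can predate background therapy. In patients who started or changed that therapy inside the window, a pre-dose fall can enter the primary NRS change, CRP normalization at 8 and 26 weeks, time to normalization and percent CRP change.

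It does not follow that background response is in fact being credited to CardiolRx. That depends on how many patients changed therapy in the window and how far they improved before the first dose, and the documents report neither. The ranges above (0.2–2.0 NRS points on the mean; 28–82% of an early CRP) rest on assumed shares and kinetics and show only what is possible. The point deserves action because the correction is cheap, not because a large bias has been shown.

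**What to change.** 1. **CRP.** Amend Protocol 6.1, the Visit 1 footnote and Appendix 17.2 footnote 10 so that CRP is measured at Visit 1 in every patient, on the bloods already drawn. Keep the earlier value as the qualifying CRP. Use the pre-dose value closest to the first dose as baseline, so that Protocol 6.1 and SAP 8.3 agree. Report the CRP endpoints for patients with qualifying CRP ≥ 1.0 mg/dL and for those with Visit 1 CRP ≥ 1.0 mg/dL. This repairs CRP only. Because Visit 1 may precede Day 1 by up to 72 hours, it narrows the gap rather than closing it.
2. **Pain and CRP tables.** Add to SAP Tables 16–20 a descriptive split by whether any NSAID, colchicine or corticosteroid was started or, where recorded, increased in the 7 days before Day 1. The one-month medication history at Visit 1 and the records required by Protocol 9.2.8 supply the dates. Read the group without such a change as the cleaner estimate. This also serves patients already enrolled, and the SAP is to be signed before the Week 8 analysis. State how incomplete start dates are classified.
3. **Consistency.** Reconcile the synopsis, criterion 5 and Protocol 6.6 on duration of background therapy, and check the result against the 7-day baseline window. No duration is proposed here.

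The cost is one assay per patient on existing blood and one split from collected dates. The drawbacks are small subgroups among about 25 patients, possibly smaller reported falls, and fewer patients with baseline CRP ≥ 1.0 mg/dL when the Visit 1 value is used.
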